13.8 Patient removal from study

Patients may be removed from treatment on this study for any of the following reasons:

- Progression of disease
- Noncompliance with study procedures
- Patient's request to withdraw from the study or refusal of further therapy
- Unacceptable adverse events: A patient may be removed from the study for any complication of treatment that the investigator feels is life threatening
- Investigator discretion
- Dose delay >28 days for treatment related AE NOTE: If a patient has clinical benefit from the study treatment, patient may continue on study at investigator discretion

14.0 Body Fluid Biospecimens

14.1 Summary Table of Research Blood and Body Fluid Specimens to be Collected for this Protocol

Biospecimen	Mandatory or optional	Timing	Correlative science justification	Information on submission
EDTA tube (whole blood)	Mandatory	Serial draws	circulating biomarker work	Section 14.2 and 14.3
Streck cfDNA BCT (whole blood)	Mandatory	Serial draws	cfDNA based studies	Section 14.2 and 14.3
AccuCyte tube (whole blood)	Mandatory	Serial draws	CTC based studies	Section 14.2 and 14.3

14.2 Collection and Processing

14.21 Sample collection should be restricted to Monday – Thursday. However, if the subject can only be seen on a Friday, please contact the Biospecimen Resource Manager for additional instructions (see protocol resource pages for contact information).

14.22 Specimen tube(s) must be labeled with the protocol number, study patient ID number, and the time and date of the blood draw.

14.23 Blood/blood products must be collected and shipped according to specific instructions provided in the kit and the table below.

Collection tube	Volume to collect per tube (number of tubes to collect)	Blood product being processed and submitted	Timepoints			Additional processing required at site	Storage and shipping conditions
			Baseline Cycle 1 Day 1**	Cycle 3 Day 1	End of treatment		
EDTA tube (purple top)	10 mL (1)	Whole blood for DNA, buffy coat, WBCs and plasma*	X	X	X	Yes	Frozen on dry ice
Streck cfDNA BCT tube	10 mL (2)	Whole blood for platelet poor plasma	X	X	X	None	Ship same day at ambient temperature
AccuCyte tube	10 mL (1)	Whole blood for CTCs	X	X	X	None	Ship same day at ambient temperature

* DNA extraction from whole blood to be done at each site

** Baseline samples may be procured any time after registration and prior to treatment on C1D1

14.24 Shipping

14.241 Verify that ALL sections of the Blood Specimen Submission Form (see Forms Packet), BAP Requisition Form (provided in kit), and specimen collection labels are completed and filled in correctly. Enter information from the Blood Specimen Submission Form into the remote data entry system within 7 days after specimen collection (see Forms Packet).

14.242 Specimens collected in the Streck cfDNA BCT and AccuCyte tubes should be shipped at ambient temperature on the same day they are drawn.

14.243 Specimens collected in EDTA tubes should be processed for DNA from whole blood, a buffy coat back up and plasma aliquots then stored frozen. NOTE: DNA extraction must be done at site where it's collected.

14.244 Samples should be shipped to BAP Freezer Mondays – Thursdays according to kit instructions. Samples should not be sent on weekends or just prior to federal holidays. (If samples can only be shipped on Fridays, please contact the Biospecimen Resource Manager for additional instructions.)

14.25 Processing

BAP Shared Resource will process the specimens.

- 14.251 Double spun, platelet poor plasma will be derived from the Streck cfDNA BCT tubes using established laboratory processes, and stored at -70°C by BAP.
- 14.252 DNA will be extracted from whole blood, and white blood cells and plasma will be derived from remaining blood from the EDTA tubes, divided into aliquots, and stored at -70°C by BAP according to patient consent information.
- 14.253 Whole blood collected in the AccuCyte tubes will be provided directly to [name] laboratory at Mayo Clinic Rochester to isolate and retain CTCs.
- 14.254 As part of ongoing research at the Mayo Clinic, we will retain residual whole blood, white blood cells, CTCs, DNA, and plasma for future research studies, according to patient consent information. Samples will be stored until specific analyses are identified and may be used for exploratory biomarker analyses, validation studies, or potential diagnostic development. As protocols are developed, they will be presented for IRB review and approval.

14.3 Background and Methodology

14.31 ctDNA

Detection of cancer specific mutations from the peripheral blood is an area of active investigation in many different type of cancers. An accumulating body of literature confirms an excellent correlation between mutations found in cancer tissues and mutations detected in cfDNA from the same patients.(Kim, Lee et al. 2015) Changes in cfDNA also correlate well with tumor marker dynamics in serial sampling, suggesting that cfDNA mutant allele fraction changes reflect changes in disease burden over time and treatment. Plasma based DNA mutation detection should therefore provide longitudinal changes in the representative genomic landscape of the malignancy in a non-invasive manner, overcoming the two major limitations of tissue based DNA mutation analysis (invasiveness and limited sampling from a genetically heterogenous tumor).(Diehl, Li et al. 2005; Diehl, Schmidt et al. 2008; Dawson, Tsui et al. 2013)

10 mL whole blood samples will be collected in Streck cfDNA BCT tubes. These specimens will be shipped immediately at ambient temperature to Mayo Clinic Rochester and then processed to aliquots of platelet poor plasma within 7 days of collection using standard protocols. Samples will be stored until we are ready for DNA extraction and mutational analysis.

Mutation analysis will be performed on the baseline cfDNA samples including FGFR and Her-2. Selected mutations identified at baseline will be verified and quantified in all cfDNA samples using ultrasensitive digital droplet PCR based assays.

14.32 CTCs

That CTCs have biologic relevance in epithelial malignancies is

increasingly clear, as their relative abundance in the peripheral blood has strong correlations with disease related outcomes in early stage and advanced breast cancer.(Cristofanilli, Budd et al. 2004; Hayes, Cristofanilli et al. 2006; Liu, Shields et al. 2009; Bidard, Peeters et al. 2014; Liu 2014; Campton, Ramirez et al. 2015)¹⁻⁵ Beyond simple enumeration, molecular profiling of these cells may provide clinically relevant predictive information to guide the selection of therapy. Deriving detailed molecular signatures for isolated CTCs may also facilitate drug discovery by assessing the markers unique to progression, such that relapsing patients may be treated for their current molecular disease.

The RareCyte CTC technology is a comprehensive, reproducible and highly sensitive dual-platform for collecting, identifying and analyzing CTCs that does not rely on EpCAM expression for enrichment.⁶ The front end AccuCyte system is based fundamentally on the density of CTCs, which is within the range of the buffy coat; a unique separation tube and collector device allow for virtually complete harvesting of the buffy coat into a small volume for application to a microscopic slide without cell lysis or wash steps, a potential source of CTC loss. The follow-up CyteFinder system is an automated scanning digital microscope and image analysis system that presents high-resolution images of candidate cells stained with well-characterized markers before definitive classification as a CTC. Importantly, CyteFinder includes an integrated device (CytePicker™) for CTC retrieval that is mechanically precise, enabling the isolation of DNA derived from single or pooled CTCs advanced genomic analyses including the detection of specific mutations and targeted NGS. The Mayo group has established experience detecting and isolated purified CTCs from breast cancer patients, as well as the capability to design 4- or 6-marker panels to capture specific phenotypic populations of CTCs.

10 mL whole blood samples will be collected in AccuCyte Blood Collection Tubes, which contain the proprietary RareCyte cell preservative. These samples will be shipped immediately at ambient temperature to Mayo Clinic Rochester and then processed through the RareCyte system within 3 days of collection. CTCs will be captured onto glass slides (8 slides per blood sample) for subsequent immunofluorescent staining, selection, and single cell isolation. The markers used for CTC identification will include DAPI or SYTOX orange, cytokeratin, and EpCAM at a minimum. CD45 will be used to distinguish WBCs (CD45 positive) from CTCs (CD45 negative). Pure populations of CTCs will then be isolated and stored for subsequent molecular analyses, as yet to be determined.

15.0 Drug Information

15.1 FTD/TPI (TAS-102; Lonsurf®; Trifluridine (FTD) / Tipiracil hydrochloride (TPI))

15.11 Background

FTD/TPI is an orally available combination drug of an antineoplastic thymidine-based nucleoside analogue, 1M trifluridine (FTD), and 0.5 M tipiracil hydrochloride (TPI). FTD is incorporated into deoxyribonucleic acid of tumor cells following phosphorylation. TPI inhibits degradation of FTD by thymidine phosphorylase.

15.12 Formulation

FTD/TPI contains trifluridine (FTD) and tipiracil (TPI as active ingredients with a molar ratio of 1:0.5. TAS-102 drug products are immediate-released film coated tablets, with two strengths of 15 mg and 20 mg (expressed as FTD). The inactive ingredients of the TAS-102 15 mg and 20 mg tablets are lactose monohydrate, pregelatinized starch, stearic acid, hypromellose, polyethylene glycol, titanium dioxide, red ferric oxide (only 20 mg tablet), and magnesium stearate.

FTD/TPI (TAS-102) tablet (15 mg) contains 15 mg FTD and 7.065 mg TPI as active ingredients. The appearance is white round tablet.

FTD/TPI (TAS-102) tablet (20 mg) contains 20 mg FTD and 9.42 mg TPI as active ingredients. The appearance is pale red round tablet.

15.13 Preparation and storage

Store at 20°C to 25°C (68°F to 77°F); excursions are permitted from 15°C to 30°C (59°F to 86°F). If stored outside of original bottle, discard after 30 days

15.14 Administration

Recommended to take within 1 hour after completion of the morning and evening meals.

15.15 Pharmacokinetic information

Protein Binding: Trifluridine: >96% (primarily to albumin); Tipiracil: <8%

Metabolism: Trifluridine and tipiracil are not metabolized by cytochrome P450 (CYP) enzymes. Trifluridine is mainly eliminated by metabolism via thymidine phosphorylase to form an inactive metabolite, 5-(trifluoromethyl) uracil (FTY)

Half-life elimination: Trifluridine: 2.1 hours (at steady state); Tipiracil: 2.4 hours (at steady state)

Time to peak, plasma: ~2 hours

Excretion: Trifluridine: Urine (<2% [as unchanged drug]; ~19% [as inactive metabolite FTY]); Tipiracil: Urine (~29% [as unchanged drug]).

15.16 Potential Drug Interactions

Caution is required when using drugs that are human thymidine kinase substrates, e.g., zidovudine. Such drugs, if used concomitantly with FTD/TPI, may theoretically compete with the effector of FTD/TPI, i.e., FTD, for activation via thymidine kinases. Therefore, when using antiviral drugs that are human thymidine kinase substrates, monitor for possible decreased efficacy of the antiviral agent, and consider switching to an alternative

antiviral agent that is not a human thymidine kinase substrate such as: lamivudine, zalcitabine, didanosine, abacavir, etc.

15.17 Known potential adverse events:

Very common known potential toxicities, ≥10%:

Blood and lymphatic: Anemia, leukopenia, neutropenia, thrombocytopenia

Gastrointestinal: Diarrhea, nausea, vomiting

General: Fatigue

Metabolism and nutrition: Decreased appetite

Common known potential toxicities, ≥1% - <10%

Blood and lymphatic: Febrile neutropenia, lymphopenia, monocytosis

Dermatologic: Alopecia, dry skin, Palmar-plantar erythrodysesthesia syndrome, pruritis, rash

Gastrointestinal: Abdominal pain, constipation, oral disorder, stomatitis

General: Malaise, mucosal inflammation, edema, pyrexia

Hepatobiliary: Hyperbilirubinemia

Infections: Lower respiratory tract infection, upper respiratory tract infection

Investigations: Blood alkaline phosphatase increased, hepatic enzyme increased, weight decreased

Metabolism and nutrition: Hypoalbuminemia

Nervous System: Dizziness, dysgeusia, headache, peripheral neuropathy

Psychiatric: Insomnia

Renal and urinary: Proteinuria

Respiratory: Cough, dyspnea

Vascular: Flushing

Uncommon known potential toxicities, <1% (Limited to important or life-threatening):

Blood and lymphatic: Pancytopenia

Gastrointestinal: Ascites, colitis, ileus, acute pancreatitis, subileus

General: General physical health deterioration

Infections: Bacterial infection, biliary tract infection, enteritis infection, urinary tract infection

Investigations: Blood lactate dehydrogenase increased

Metabolism and nutrition: Dehydration

Respiratory: Pulmonary embolism

15.18 Drug procurement

FTD/TPI (TAS-102) will be provided free of charge by Taiho Oncology.

15.19 Nursing Guidelines

- 15.191 Instruct Patients to take FTD/TPI (TAS-102) within 1 hour after morning or evening meal with a glass of water. Patients will not make up for a missed dose. If a patient vomits after taking the study medication, the dose should not be replaced.
- 15.192 Patients may experience fatigue. Instruct patients in energy conserving lifestyle.
- 15.193 GI side effects are common, including nausea, decreased appetite, diarrhea, vomiting, and abdominal pain.
- 15.194 Cytopenias are common. Monitor CBC w/diff and instruct patients to report any signs or symptoms of infection and/or unusual bruising or bleeding to the study team.
- 15.195 Rarely Pulmonary embolism has been reported with this agent. Instruct patient to report any shortness of breath or chest pain to study team and/or seek out emergency medical attention.
- 15.196 Although uncommon, warn patients of the possibility of alopecia.

16.0 Statistical Considerations and Methodology

16.1 Overview

This protocol will assess the efficacy of FTD/TPI (TAS-102) in patients with refractory cholangiocarcinoma using a single stage phase II study design. This single arm Phase II trial will assess the 16-week progression-free survival rate (by RECIST v1.1) associated with FTD/TPI (TAS-102) in patients with refractory cholangiocarcinoma. We will adopt a PFS rate of 10% as the null hypothesis and PFS rate of 30% as the alternative hypothesis. In addition to response, this study will also evaluate the overall response rate (ORR), progression-free survival (PFS), overall survival (OS), and adverse events.

16.11 Primary Endpoint

The primary endpoint for this study is 16-week progression-free survival associated with FTD/TPI (TAS-102) in patients with refractory cholangiocarcinoma.

16.2 Statistical Design:

16.21 Decision Rule

The largest success proportion where the proposed treatment regimen would be considered ineffective in this population is 10%, and the smallest success proportion that would warrant subsequent studies with the proposed regimen in this patient population is 30%. The following single stage design uses 25 patients to test the null hypothesis that the true success proportion in a given patient population is at most 10%. If 5 or fewer successes are observed in the 25 evaluable patients, we will consider this regimen ineffective in this patient population. If 6 or more successes are observed in the 25 evaluable patients, we may recommend further testing of this regimen in subsequent studies in this population.

NOTE: We consider a success to be alive and progression-free by 16 weeks post-registration (i.e. stable disease, partial response, or complete response).

16.22 Sample Size:

The single stage study design to be utilized is fully described in Section 16.21. A maximum of 25 evaluable patients will be accrued onto this phase II study unless undue toxicity is encountered. We anticipate accruing an additional 3 patients to account for ineligibility, cancellation, major treatment violation, or other reasons. Maximum projected accrual is therefore 28 patients.

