1.4 Study Design

This is the single arm phase II trial to assess the efficacy of FTD/TPI in advanced, refractory BTCs. The primary end point of this study is 16-week progression-free survival. If 30% of patients remain progression-free at 16-weeks, this trial will be considered a success warranting bigger trials. We will accrue 25 evaluable patients using a single stage design. The total sample size of this study is 28 to account for 3 possible non-evaluable subjects.

Patient will receive FTD/TPI at the dose of 35 mg/m² on Days 1-5 and 8-12 of 28-day cycle. Patient will receive treatment until disease progression or unacceptable toxicities. Patients will undergo restaging scans every 2 cycles. Subjects will be monitored for adverse events from the beginning of the study drug to 28 days after the last dose. We will collect blood samples for determination of cell free DNA and circulating tumor cells at baseline, after 2 cycles and at progression.

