13.5 Definition of Ineligible

A patient is deemed *ineligible* if after registration, it is determined that at the time of registration, the patient did not satisfy each and every eligibility criteria for study entry. The patient may continue treatment off-protocol at the discretion of the physician as long as there are no safety concerns, and the patient was properly registered. The patient will go directly to the event-monitoring phase of the study (or off study, if applicable).

- If the patient received treatment, all data up until the point of confirmation of ineligibility must be submitted. Event monitoring will be required per Section 18.0 of the protocol.
- If the patient never received treatment, on-study material must be submitted. Event monitoring will be required per Section 4.0 of the protocol.

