13.6 Definition of Major Violation

A patient is deemed a *major violation*, if protocol requirements regarding treatment in cycle 1 of the initial therapy are severely violated that evaluability for primary end point is questionable. All data up until the point of confirmation of a major violation must be submitted. The patient will go directly to the event-monitoring phase of the study. The patient may continue treatment off-protocol at the discretion of the physician as long as there are no safety concerns, and the patient was properly registered. Event monitoring will be required per Section 4.0 of the protocol.

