13.7 Definition of Cancel

A patient is deemed a *cancel* if he/she is removed from the study for any reason before any study treatment is given. On-study material and the End of Active Treatment/Cancel Notification Form must be submitted. No further data submission is necessary.

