16.31 Primary Endpoint

16.311 **Definition:** The primary endpoint of this trial is the progression-free survival rate. This is defined as the proportion of evaluable patients who are progression-free (stable disease, partial response, complete response) at 16 weeks. All patients meeting the eligibility criteria who have signed a consent form and have begun treatment will be considered evaluable.

16.312 **Estimation:** The proportion of successes will be estimated by the number of successes divided by the total number of evaluable patients. Confidence intervals for the true success proportion will be calculated according to the approach of Clopper and Pearson.

16.316 **Over Accrual:** If more than the target number of patients are accrued, the additional patients will not be used to evaluate the stopping rule or used in any decision making processes; however, they will be included in final point estimates and confidence intervals as though they were accrued in the final stage.

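### Does the accrual allowance for major treatment violations leave it unclear which 25 patients decide the primary endpoint?

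*Combined protocol and SAP*

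**What the plan says.** All references are to the combined protocol and SAP.

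- **16.311 (Definition, under Primary Endpoint in the analysis plan):** "All patients meeting the eligibility criteria who have signed a consent form and have begun treatment will be considered evaluable". No exception is made for violations.
- **16.312 (Estimation):** "The proportion of successes will be estimated by the number of successes divided by the total number of evaluable patients".
- **16.21 (Decision Rule):** 5 or fewer successes in the 25 evaluable patients means ineffective; 6 or more may lead to further testing.
- **16.22 (Sample Size):** at most 25 evaluable patients, then "We anticipate accruing an additional 3 patients to account for ineligibility, cancellation, major treatment violation, or other reasons", giving 28.
- **1.4 (Study Design):** "The total sample size of this study is 28 to account for 3 possible non-evaluable subjects". No reasons are listed.
- **13.5, 13.6 and 13.7:** an ineligible patient is one for whom, at registration, "the patient did not satisfy each and every eligibility criteria for study entry". A major violator is one whose cycle 1 treatment requirements were so "severely violated that evaluability for primary end point is questionable". A cancel is "removed from the study for any reason before any study treatment is given".
- **16.316 (Over Accrual):** beyond the target number, "the additional patients will not be used to evaluate the stopping rule or used in any decision making processes", although such patients do enter the final estimate and confidence interval.

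**The concern.** Two of the reasons in 16.22 fit 16.311 exactly: an ineligible patient fails the eligibility condition, and a cancel never began treatment. The other two, major treatment violation and unspecified other reasons, do not fit. A major violator is defined by what happened in cycle 1, so has normally started treatment and is evaluable under 16.311 if eligible. Yet 16.22 and 1.4 together suggest a patient who needs replacing, and 13.6 calls evaluability questionable without settling it.

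If a violator could be dropped and replaced, the choice of the 25 could be made after treatment has begun, in a single-arm trial where one patient can change the decision. For example, suppose three violators, all failures, are among the first 25 treated, the other 22 have 5 successes, and patients 26 to 28 have 1. Keeping the violators gives 5/25 (ineffective). Replacing them gives 5 + 1 = 6 of 25 (may recommend further testing).

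**Working it through.** **1. The plan's own figures.** The inputs are n = 25, success at 6 or more, null 10% and alternative 30% (16.21). P(X ≥ 6 | 25, p) is 0.0334 at p = 0.10, 0.1615 at 0.15, 0.3833 at 0.20, 0.6217 at 0.25 and 0.8065 at 0.30. The table in 16.24 gives 0.033, 0.160, 0.383, 0.622 and 0.807. The figures at 10% and 30% reproduce, and the difference at 15% is immaterial. Accrual is 25 + 3 = 28, as stated.

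**2. Which text sets the denominator.** Section 16.311 is headed as a definition and is unqualified. Section 16.312 divides by the set it defines, and 16.21 counts successes in 25 patients described by the same word. Section 16.22 says how many patients the sponsor expects to register; it does not say a violator is excluded or replaced. After raising the question of evaluability, 13.6 deals with data submission, event monitoring and off-protocol treatment. It contains no exclusion rule.

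**3. Result of following the plan.** Violators stay in. If the 10% and 30% are rates over all evaluable patients, as 16.311 implies, type I error is 0.033 and power 0.807. Now fix m of the 25 as violators who all fail, and hold the overall rate at 30%. Power is P(X ≥ 6 | 25 − m, 0.30 × 25/(25 − m)) = 0.809, 0.811 or 0.814 for m = 1, 2, 3. Power does not fall.

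**4. Result of departing from it.** The documents do not give m, so the range is 1 to 3, bounded by the allowance. Suppose the overall rate is 10% and m treated failures are dropped and replaced. Successes are then counted over 25 + m treated patients, so type I error is P(X ≥ 6 | 25 + m, 0.10) = 0.040, 0.047 or 0.055. Using the fixed-m model of step 3 instead, it is P(X ≥ 6 | 25, 0.10 × 25/(25 − m)) = 0.0397, 0.0475 or 0.0570. Either way only m = 3 exceeds the stated 0.05. If exclusion is unrelated to outcome, it stays at 0.033.

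**5. How often the two readings would disagree.** The ranges cover violators who all fail (10% or 30% taken over non-violators or over all treated) and violators who succeed at the same rate as other patients.

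| m | True 10% | True 30% |
|---|---|---|
| 1 | 0.006–0.010 | 0.032–0.049 |
| 2 | 0.011–0.018 | 0.062–0.080 |
| 3 | 0.015–0.025 | 0.088–0.120 |

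**6. The estimate.** With 6 successes in 28 eligible treated patients, the plan's estimate is 6/28 = 21.4% (Clopper-Pearson 95% CI 8.3–41.0%). Dropping three failing violators would give 6/25 = 24.0% (9.4–45.1%).

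**7. The example re-read.** Under 16.311 the 25th eligible treated patient completes the set. Patients 26 to 28 would then be treated only through over-accrual, which 16.316 keeps out of the decision, or because the exclusion reading had already been applied during accrual. The same holds for 6/28. Both cases are possible, but neither is the plan's normal course.

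**The case for a change.** The best argument for a change is that an allowance for eligible treated violators has no purpose if they count towards the 25. Its presence in 16.22, and the description of the three extras in 1.4 as non-evaluable, would then show that someone meant to exclude them. No sentence states that 16.311 takes precedence. Section 16.316 does not help, because who is beyond target depends on whether the violator counted. Section 13.6 sets no objective threshold and no deadline for declaring a violation.

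There is also a scenario in which keeping violators costs power. If 30% is the rate among non-violators only and all m violators fail, power is P(X ≥ 6 | 25 − m, 0.30) = 0.771, 0.731 or 0.687, with type I error of 0.028, 0.023 or 0.018.

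Some of this stands. The wording is loosely inconsistent, and the unspecified other reasons are never defined. But a cautious accrual forecast does not override an unqualified definition placed in the analysis plan for the primary endpoint. Exclusion has to be inferred by joining 16.22 to 13.6, and neither states it. The violation category is also confined to cycle 1 treatment (28 days), while restaging comes every two cycles, which limits outcome-driven reclassification without ruling it out. The power-loss scenario uses a success rate defined over a population other than the one in 16.311, and its error is conservative.

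**Conclusion.** The concern does not hold as a reason to change the plan. Section 16.311 settles the status of an eligible treated major violator: the patient is evaluable, is in the denominator of 16.312, and counts towards the 25 in 16.21. An analyst following the text gets the tabulated 0.033 and 0.807, provided the 10% and 30% are read as rates over all evaluable patients.

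Harm requires acting against that definition. Even then, type I error passes 0.05 only if the whole allowance of three is spent on treated violators who all fail and are replaced (0.055 to 0.057). That is an extreme case, because the same three places must also cover ineligibility, cancellation and other reasons. With one violator, the readings would lead to different decisions with probability of at most 0.010 at a true 10% and 0.049 at a true 30%.

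A sentence confirming that such a patient stays evaluable would be harmless and optional. It would restate the existing rule without changing the decision or the estimate. A sensitivity analysis excluding violators is a matter of preference.
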